9.2.3 Analysis of Safety

The assessment of safety will be based primarily on the frequency of patients with adverse events and clinical laboratory abnormalities. Other safety data will be summarized as appropriate.

All safety analyses will be conducted on the total patient cohort based on the Safety Population.

Adverse events will be coded using the Medical Dictionary for Regulatory Activities. Reports will be provided to the Medical Monitor for approval of the coded terms after the database is clean, prior to unblinding. The number and frequency of patients with TEAEs (ie, those adverse events that newly occur or worsen in severity during the study) will be summarized by system organ class and preferred term. Serious adverse events and TEAEs related to study drug will be summarized in the same manner. A list of patients with SAEs and those who discontinue from the study due to an adverse event will be provided.

Summary statistics by treatment group at baseline, at all post-randomization visits, and changes from baseline to the post-randomization visits for laboratory values will be provided. Occurrence of significant abnormalities in laboratory values from baseline will be summarized by treatment group. Vital signs, body weight, and physical examination findings will be summarized.

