For continuous secondary efficacy variables, the same ANCOVA model will be used as the primary efficacy analysis. For categorical data, logistic regression or chi-square test will be used. Treatment effects will be evaluated between KBP-5074 doses and placebo.

Safety assessments will include monitoring of adverse events, vital signs (pulse rate, respiratory rate, and oral temperature), clinical laboratory findings, 12-lead ECGs, and physical examination findings. All safety analyses will be conducted on the total patient cohort based on the Safety Population.

The assessment of safety will be based primarily on the frequency of patients with adverse events and clinical laboratory abnormalities. Other safety data will be summarized as appropriate.

Adverse events will be coded using the Medical Dictionary for Regulatory Activities. Reports will be provided to the Medical Monitor for approval of the coded terms after the database is clean, prior to unblinding. The number and frequency of patients with treatment-emergent adverse events (TEAEs) (ie, those adverse events that newly occur or worsen in severity during the study) will be summarized by system organ class and preferred term. Serious adverse events (SAEs) and TEAEs related to study drug will be summarized in the same manner. A list of patients with SAEs and those who discontinue from the study due to an adverse event will be provided.

Summary statistics by treatment group at baseline, at all post-randomization visits, and changes from baseline to the post-randomization visits for laboratory values will be provided. Occurrence of significant abnormalities in laboratory values from baseline will be summarized by treatment group. Vital signs, body weight, and physical examination findings will be summarized.

The analysis of the PK/PD relationship will be explored. Population PK models will be built using a nonlinear mixed effects modeling technique with NONMEM software based on the PPK Population. Different PK models will be attempted to fit the PK concentration-time data. After the PPK modeling, a population PD approach will be used to explore the concentration-effect relationships. Different PD models will be attempted to fit the concentration-effect data. All PD exploration will be based on the ITT Population.

SAMPLE SIZE DETERMINATION:

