3 STUDY DESCRIPTION

3.1 Summary of Study Design

This is a Phase 2, randomized, double-blind, placebo-controlled, multi-center study to assess the efficacy, safety, and PK of KBP-5074 in patients with moderate-to-severe CKD and uncontrolled hypertension (Grade 1 to 2 systolic hypertension – ESC/ESH).

The study will enroll approximately 240 patients, randomized in a 1:1:1 ratio to 1 of 3 treatment groups (80 patients in each group): KBP-5074 0.25 mg QD, KBP-5074 0.5 mg QD, or placebo QD. Randomization will be stratified to balance enrollment for key variables that may influence safety and/or efficacy evaluations, including eGFR (\geq 30 versus < 30 mL/min/1.73 m²) and SBP (\geq 160 versus < 160 mmHg). Approximately 30% of patients enrolled in the study should have eGFR in the range of 15 to 29 mL/min/1.73 m². The study will be approximately 5 months in duration with 84 days of double-blind treatment.

The study will consist of up to a 4-week screening period, 2-week open-label (placebo) run-in period, 84-day double-blind treatment period, and a 4-week post-treatment safety follow-up period.

Plasma samples for PK analysis will be collected from all patients. A total of 4 PK samples will be collected from each patient, including at Day 1 (prior to discharge), Day 14 pre-dose, Day 28 pre-dose, and the End of Study Visit (Day 112)/Early Termination Visit. The pre-dose samples assume that patients will be dosed in the unit on the days above. If patients are not dosed in the unit on those days, a PK sample will be collected during each of these visits and the date and time of the last dose will be recorded.

Safety will be assessed systematically, and an independent data monitoring committee (IDMC) will perform cumulative reviews of safety data at regular intervals during the study.

Serum potassium levels, serum creatinine, and blood pressure will be closely monitored throughout the study and clinically significant changes will be reported as adverse events of special interest.

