5 STUDY TREATMENTS

5.1 Treatment Groups

After completion of the screening period and qualifying Screening Visit, patients who meet all eligibility criteria (except those criteria scheduled to be assessed after the Screening Visit) will enter a 2-week run-in period. During this time, all patients will be given open-label placebo.

At the Day 1 Visit (scheduled within 4 ± 2 days after the end of the run-in period [Visit 3]), eligible patients will be randomized by Interactive Response Technology (IRT) in a 1:1:1 ratio to the following treatment groups:

- KBP-5074 0.25 mg QD orally,
- KBP-5074 0.5 mg QD orally, or
- Placebo QD orally

The duration of the double-blind treatment period will be 84 days. Patients will remain on their stable antihypertensive medication (ie, no change in antihypertensive medication) throughout the entire study (including both the run-in and treatment periods). The dose of diuretic may be adjusted based on developing or resolved edema, weight gain or loss, or pulmonary congestion.

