8.1 Adverse Events

An adverse event is defined as any untoward medical occurrence in a clinical investigation patient administered a pharmaceutical product, which does not necessarily have a causal relationship with this treatment. An adverse event can therefore be any unfavorable and/or unintended sign (including an abnormal laboratory finding), symptom, or disease temporally associated with the use of an investigational medicinal product, whether or not related to the investigational medicinal product. All adverse events, including observed or volunteered problems, complaints, or symptoms, are to be recorded on the appropriate eCRF.

Adverse events, which include clinical laboratory test variables, will be monitored and documented from the time of informed consent until study participation is complete. Patients should be instructed to report any adverse event that they experience to the Investigator. Beginning with the Screening Visit, Investigators should make an assessment for adverse events at each visit and record the event on the appropriate adverse event eCRF.

Wherever possible, a specific disease or syndrome rather than individual associated signs and symptoms should be identified by the Investigator and recorded on the eCRF. However, if an observed or reported sign or symptom is not considered a component of a specific disease or syndrome by the Investigator, it should be recorded as a separate adverse event on the eCRF. Additionally, the condition that led to a medical or surgical procedure (eg, surgery, endoscopy, tooth extraction, or transfusion) should be recorded as an adverse event, not the procedure.

Any medical condition already present at Screening should not be reported as an adverse event unless the medical condition or signs or symptoms present at baseline changes in severity or seriousness at any time during the study. In this case, it should be reported as an adverse event.

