8.2 Adverse Events of Special Interest

The following adverse events of special interest must be reported to the Sponsor within 24 hours of the Investigator's awareness, even if not meeting the definition of an SAE:

- Hyperkalemia;
 - Mild hyperkalemia defined as serum potassium 5.0 mmol/L to 5.5 mmol/L (central or local laboratory);
 - o Moderate hyperkalemia defined as serum potassium 5.6 mmol/L to 5.9 mmol/L (central or local laboratory); and
 - o Severe hyperkalemia defined as serum potassium $\geq 6.0 \text{ mmol/L}$;
- Reduction from Day 1 eGFR levels \geq 30% throughout the duration of the study;
- Hypertensive emergency;
 - Defined as confirmed (based on the mean of at least 2 current consecutive protocol-required blood pressure readings, or otherwise obtained blood pressure readings) with SBP > 180 mmHg and/or DBP > 120 mmHg with associated new or progressive target organ damage, neurologic, and/or cardiac symptoms. Blood pressures of > 200 mmHg in asymptomatic patients should be recorded in the eCRF, and Investigators must differentiate between hypertensive urgency (markedly elevated blood pressure) and emergency. See Section 8.14 and Appendix C for definition and management of hypertensive emergencies and urgencies; and
- Symptomatic hypotension, or if the SBP < 90 mmHg after the first dose of study drug at Day 1.

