9 STATISTICS

9.1 Analysis Populations

The Intent-to-Treat (ITT) Population will consist of all randomized patients who take at least 1 dose of randomized study drug, have a baseline SBP measurement, and have at least 1 post-randomization SBP measurement. The ITT Population is the primary analysis population. All efficacy analyses will be performed for the ITT Population.

The Per-Protocol Population will include all ITT patients who have completed the 84-day double-blind treatment period without any major protocol deviations or violations. The Per-Protocol Population will be used to assess robustness of the primary analysis results. The major protocol deviations will be pre-specified prior to unblinding treatment codes for analyses.

The Safety Population will include all randomized patients who receive at least 1 dose of randomized study drug.

The PPK Population will include all randomized patients who receive at least 1 dose of randomized study drug and have at least 1 measurable concentration of total KBP-5074.

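### The treatment-emergent AE definition states no first-dose start and no end, and the yes/no causality definitions leave some events unclassified and conflict with Section 8.1.1

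*Combined protocol and SAP*

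**What the plan says.** **TEAE window.** The definition in Section 9.2.3 is "those adverse events that newly occur or worsen in severity during the study". The synopsis uses the same words: "treatment-emergent adverse events (TEAEs) (ie, those adverse events that newly occur or worsen in severity during the study". Neither names a first dose or an end date.

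**Collection.** Under Section 8.1, adverse events "will be monitored and documented from the time of informed consent until study participation is complete". They are recorded at Visits 1, 2 and 3 (Sections 6.2, 6.3.1 and 6.3.2), all before the first randomised dose. One filter applies: "Any medical condition already present at Screening should not be reported as an adverse event unless" the condition changes in severity or seriousness.

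**Population.** Section 9.1: "The Safety Population will include all randomized patients who receive at least 1 dose of randomized study drug". This selects patients, not event dates.

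**Usage of terms.** Section 5.1 expressly includes both the run-in and the treatment periods in the whole study. Sections 6.3.1 and 6.3.2 call the run-in placebo study drug.

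**First-dose anchors elsewhere.** Baseline (Section 9.2.1) and exposure and new concomitant medications (Section 9.2.1.1) are tied to the first dose. So is the low systolic pressure criterion in Section 8.2, which counts values under 90 "mmHg after the first dose of study drug at Day 1".

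**Causality.** Section 8.1.3 offers only Yes or No. No requires timing that excludes causality together with a suspected other cause. Yes requires compatible timing together with no other identifiable cause. The same section then says the definition implies a reasonable possibility. Section 8.1.1 treats an event as a reaction if a relationship cannot be excluded.

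**The concern.** Section 9.2.3 bases the safety assessment mainly on how many patients have adverse events and laboratory abnormalities, and the TEAE tables are the adverse-event half of that. A programmer following the stated definition would count events from screening and the run-in under the arm assigned later. Those events occur before randomisation, so on average they are balanced across arms. They raise every arm's incidence and shrink the difference between drug and placebo. Dilution toward no difference is the unhelpful direction for a safety table.

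The causality wording has a different consequence. An event with compatible timing and another possible cause is plausible in patients with chronic kidney disease on several background drugs, and it meets neither definition. Investigators could code identical events differently. This feeds the table of related TEAEs (Section 9.2.3) and the reporting of related serious events more than 30 days after the last dose (Section 8.4).

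**Working it through.** The plan states no figure on this point, so there is none to reproduce.

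**1. Pre-dose share of collection time**

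Inputs:
- Section 3.1: "up to a 4-week screening period, 2-week open-label (placebo) run-in period", that is up to 28 days plus 14 days, followed by 84 days of treatment and 28 days of follow-up.
- Section 5.1: the Day 1 visit falls 4 ± 2 "days after the end of the run-in period [Visit 3]), eligible patients will be randomized", a gap of 2 to 6 days.
- Appendix A: Visit 1 at ≤ -42 days, Visit 2 at ≤ -18, Visit 3 at ≤ -4.

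Post-dose time is 84 + 28 = 112 days. Share = d / (d + 112), where d is pre-dose days.

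| Case | d | Share |
|---|---|---|
| Negligible screening, shortest gap: 14 + 2 | 16 | 16/128 = 12.5% |
| Appendix A read as a cap at Day -42 | 42 | 42/154 = 27.3% |
| Sections 3.1 and 5.1 added, shortest gap: 28 + 14 + 2 | 44 | 44/156 = 28.2% |
| Sections 3.1 and 5.1 added, longest gap: 28 + 14 + 6 | 48 | 48/160 = 30.0% |

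The capped reading leaves 42 - 18 = 24 days for screening, against up to 28 in Section 3.1. The upper end therefore depends on how those places are reconciled.

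**2. Illustration of dilution (the event rates are assumptions)**

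Assume a constant placebo hazard and independence of pre-dose and post-dose events. With post-dose placebo rate p0, the chance of a pre-dose event is b = 1 - (1 - p0)^(d/112). The observed rate in an arm is 1 - (1 - p)(1 - b), so the risk difference is multiplied by (1 - b).

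Assumed post-dose rates of 40% and 55% (difference 15.0 points, risk ratio 1.38):

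| d | b | Observed rates | Difference | Risk ratio |
|---|---|---|---|---|
| 16 | 7.0% | 44.2% vs 58.2% | 13.9 points | 1.32 |
| 42 | 17.4% | 50.5% vs 62.8% | 12.4 points | 1.25 |
| 48 | 19.7% | 51.8% vs 63.8% | 12.05 points | 1.23 |

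For an assumed rare term at 2% vs 6% (risk ratio 3.0), the difference barely moves: 3.99 points at 16 days and 3.97 at 48. The risk ratio falls to 2.75 and 2.39.

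The relative shrinkage of the difference equals b. Over 16 to 48 days it is 3.1% to 9.1% at a 20% placebo rate, 7.0% to 19.7% at 40%, and 12.3% to 32.5% at 60%.

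**3. Causality definitions set side by side**

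| Timing | Other cause | Section 8.1.3 | Section 8.1.1 |
|---|---|---|---|
| Excludes causality | Yes | No | Not a reaction |
| Excludes causality | None | No category | Not a reaction |
| Compatible | Yes | No category | Reaction |
| Compatible | None | Yes | Reaction |

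Two of four cells have no category. In the third row, Section 8.1.1 calls the event a reaction while Section 8.1.3 withholds Yes.

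**The case against.** The term being defined is treatment-emergent, and worsening needs a reference state. Section 9.2.3 summarises laboratory data at baseline and post-randomisation visits, and Section 8.10 ties physical-examination events to findings after randomisation. Most analysts would start the window at first dose. That stands: point 1 is an ambiguity on a literal reading, and the harm arises only if the words treatment-emergent are ignored. It does not supply the anchor, because the definition is explicit and Section 5.1 puts the run-in inside the study.

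The tables are also descriptive, with no test specified. Section 8.1.3 says an event should follow study drug, which largely keeps pre-dose events out of the related-TEAE table. That protection is partial, because the run-in placebo is also called study drug.

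On causality, Section 8.1.3 describes its definition as a reasonable possibility and asks investigators to weigh concomitant disease and drugs. That moves toward Section 8.1.1 but does not remove the no-other-cause condition.

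A reader might infer more than the documents support:
- *The hyperkalaemia findings are compromised.* They are not. Potassium-threshold outputs and special-interest reporting do not depend on either definition.
- *The comparison is biased in favour of one arm.* Pre-dose events precede randomisation, so the error is non-differential.
- *The loss is a known 1 to 3 points out of 15.* Those figures rest on assumed rates. They probably overstate the effect, because conditions present at Screening count only if they change and eligibility is rechecked before dosing.
- *Related events will be under-counted.* Unclassified events could be coded either way, so the direction is unknown.

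**Conclusion.** Both points hold as drafting defects in rules the plan states, and both merit correction before unblinding.

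Point 1: the TEAE definition has no first-dose start and no end. Taken literally, it admits 12.5% to 27% pre-dose collection time if Appendix A is a cap, or up to 30% if Sections 3.1 and 5.1 are added. The lower figure assumes negligible screening time. Post-dose intent is likely, only patients later randomised and dosed are affected, and the numerical effect on risk differences is illustrative.

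Point 2: the causality categories are not exhaustive, and the Yes condition conflicts with Section 8.1.1 and with Section 8.1.3's own later sentence. It touches the related-TEAE table and related serious events after 30 days, by an unknown amount. Serious events up to 30 days after the last dose are reported whatever the causality. The primary efficacy analysis is untouched by either point.

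**What to change.** 1. In Section 9.2.3 and the synopsis, define a TEAE as an adverse event with onset, or worsening in severity, on or after the first dose of randomised study drug (not run-in placebo) through the end of the safety follow-up (Day 112 or Early Termination). List pre-dose adverse events separately.
2. Reconcile Sections 8.1.1 and 8.1.3 to one exhaustive standard: Yes if a causal relationship is a reasonable possibility, even when another possible cause exists; otherwise No.

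The cost is a few sentences in the synopsis and Sections 8.1.1, 8.1.3 and 9.2.3, with no new data or visits. The small downside is that more events may be classed as related.

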9.2.4 Analysis of Pharmacokinetics

The analysis of the PK/PD relationship will be explored. Population PK models will be built using a nonlinear mixed effects modeling technique with NONMEM software based on the PPK Population. Different PK models will be attempted to fit the PK concentration-time data. After the PPK modeling, a population PD approach will be used to explore the concentration-effect relationships. Different PD models will be attempted to fit the concentration-effect data. All PD exploration will be based on the ITT Population.

9.2.5 Interim Analysis

No interim analysis is planned.

9.2.6 Independent Data Monitoring Committee

An IDMC will be utilized in this study. The committee will consist of members external to Worldwide and KBP BioSciences. The objective of the committee is to monitor safety data on an ongoing basis. The approved IDMC charter will be on file and available for inspection as requested.

Meeting Schedule

After the organizational meeting, the IDMC will meet at least 4 times during the conduct of the study at the following treatment milestones:

- Approximately 10% of patients completed are randomized in the study,
- Approximately 25% of patients completed the 12-week treatment period,
- Approximately 50% of patients completed the 12-week treatment period, and
- Approximately 75% of patients completed the 12-week treatment period.

The analysis for the IDMC report will be conducted by an independent group not involved with the study conduct. A blinded summary of all adverse events and SAEs will be provided every 4 weeks to the IDMC and the Sponsor for ongoing safety data monitoring.

No formal inferential hypothesis testing will be conducted from the interim. The study will not stop early based on interim efficacy findings. Therefore, no further multiple testing adjustments nor any sample size adjustments will be implemented for the final analysis CIs.

9.2.7 Sample Size Determination

For this Phase 2 study, the primary efficacy endpoint is the change in trough-cuff resting seated SBP from baseline to Day 84. Assuming an observed treatment difference of SBP changes between the KBP-5074 group and the placebo group is 5 mmHg, and a standard deviation of change from baseline of 15 mmHg, with 80 patients/group, the CI of the observed difference would not include 0. Assuming 10% to 15% dropout post randomization, 80 patients/group or a total of 240 patients would be needed for this Phase 2 study. Additional sample size estimates based on sample size needed per group to ensure that the observed 95% CI does not include 0 are shown in Table 2. No multiple comparison adjustment will be applied.

Table 2. Sample Size Estimates

	Observed Treatment Effect									
Standard Deviation	4 mmHg	5 mmHg	6 mmHg							
14 mmHg	109	70	48							
15 mmHg	125	81	56							
16 mmHg	141	91	63							
Including approximately 10%	% to 15% dropout.									

Abbreviations: mmHg = millimeters of mercury.

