For this Phase 2 study, the primary efficacy endpoint is the change in trough-cuff resting seated SBP from baseline to Day 84. Assuming an observed treatment difference of SBP changes between the KBP-5074 group and the placebo group is 5 mmHg, and a standard deviation of change from baseline of 15 mmHg, with 80 patients/group, the CI of the observed difference would not include 0. Assuming 10% to 15% dropout post randomization, 80 patients/group or a total of 240 patients would be needed for this Phase 2 study. Additional sample size estimates based on sample size needed per group to ensure that the observed 95% CI does not include 0 are shown below. No multiple comparison adjustment will be applied.

Sample Size Estimates

		Observed Treatment Effect		
Standard Deviation	4 mmHg	5 mmHg	6 mmHg	
14 mmHg	109	70	48	
15 mmHg	125	81	56	
16 mmHg	141	91	63	

Including approximately 10% to 15% dropout.
Abbreviations: mmHg = millimeters of mercury

SITES:

Approximately 90 sites in North America, South America, Israel, and Europe

SPONSOR:

KBP BioSciences Co., Ltd. [name] United States

[contact] [contact]

TABLE OF CONTENTS

518	gnatur	e Page .		2
Inv	estiga	ıtor Agı	reement	3
Su	mmar	y of Ch	anges – Amendment 2	4
Sy	nopsis			17
Ta	ble of	Conten	ıts	24
Lis	st of T	ables		28
Lis	st of F	igures		29
Lis	st of A	bbrevia	ations and Definition of Terms	30
1	Intro	duction	and Background Information	32
2	Study	y Objec	tives	35
	2.1	Primar	ry Objective	35
	2.2	Secon	dary Objectives	35
3	Study Description.			36
	3.1	Summ	nary of Study Design	36
	3.2	Risk N	Management	38
		3.2.1	Independent Data Monitoring Committee.	38
	3.3	Study	Indication	38
4	Selection and Withdrawal of Patients			39
	4.1	Inclus	ion Criteria	39
	4.2	Exclus	sion Criteria	40
	4.3	Withd	rawal Criteria	42
5	Study	y Treatr	ments	44
	5.1	Treatn	nent Groups	44
	5.2	Ration	nale for Dosing	44
	5.3	Rando	mization and Blinding	44
	5.4	Breaki	ing the Blind	45
	5.5	Drug S	Supplies	45
		5.5.1	Formulation and Packaging	45
		5.5.2	Study Drug Preparation and Dispensing	46
		5.5.3	Study Drug Administration	46

		5.5.4	Treatment Compliance	46
		5.5.5	Storage and Accountability	46
	5.6	Prior	and/or Concomitant Medications and/or Procedures	47
		5.6.1	Excluded Medications and/or Procedures	47
		5.6.2	Restricted Medications and/or Procedures	47
		5.6.3	Documentation of Prior and Concomitant Medication Use	47
		5.6.4	Management of Other Co-Morbidities	48
6	Stud	y Proce	edures	49

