5.4 Breaking the Blind

At all times, study personnel will attempt to safeguard the integrity of the blinding in order to minimize bias in the conduct of the study. Breaking of the blind should not occur except in the case of a medical emergency and should occur after discussion with the Medical Monitor. In such a case, the Investigator may access this information by contacting the Sponsor or its designee. If the blind is broken for an individual patient, the blinding should be preserved for the remainder of the patients throughout the duration of the study. In such a case, study personnel may be notified of that individual patient's treatment assignment without jeopardizing study blinding for the overall study.

If the blind is broken for a patient, the patient may or may not be asked to withdraw from the study. This decision will be based on Investigator consultation with the Medical Monitor. All patients will be asked to continue study visits to the end of the study whether or not they remain on study drug. If a patient must temporarily discontinue study drug, they may or may not be able to restart study drug. This decision will be based on Investigator consultation with the Medical Monitor.

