6.4.3 Day 7 (Visit 5) ± 2 Days

The following procedures will be performed at Visit 5:

- Record weight;
- Perform 12-lead ECG in triplicate (patients should be resting in a supine position for at least 10 minutes prior to assessment);
- Obtain vital signs, including pulse rate, respiratory rate, and oral temperature;
- Obtain blood pressure prior to study drug administration;
 - Blood pressures are to be obtained according to the AHA recommendations for accurate blood pressure measurement. Patients should avoid smoking, caffeine, or exercise within 30 minutes before measurement; empty his or her bladder; then sit quietly in a comfortable

chair with back support for at least 10 minutes before measurement and remain still during the measurement. The patient's limb should be supported to measure blood pressure to ensure that the blood pressure cuff is at heart level, using the correct cuff size. Do not take the measurement over clothes. Blood pressure measurements should be performed in the same arm throughout the study. Triplicate blood pressure measurements should be taken approximately 2 minutes apart with a validated, oscillometric upper arm blood pressure monitor. Trough cuff SBP and DBP values will be assessed based on the pre-defined blood pressure measurement guideline throughout the study. Pulse will be obtained simultaneously with blood pressure measurements;

- Obtain blood sample for clinical laboratory tests (central laboratory; see Appendix B);
- Obtain urine sample for:
 - o Urinalysis (central laboratory; see Appendix B); and
 - o UACR;
- Obtain serum sample for potassium (local and central laboratories);
- Obtain serum sample for creatinine (central laboratory);
- Record adverse events and concomitant medications;
- Check study drug accountability and collect unused study drug;
- Administer daily dose of study drug and record time; and
- Instruct patient on study drug and re-dispense study drug.

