9.2.2 Analysis of Efficacy

9.2.2.1 Primary efficacy analysis

The primary efficacy analysis is to evaluate the change in trough-cuff seated SBP from baseline to Day 84 for the KBP-5074 doses compared to placebo. The endpoint for each patient is defined as the Day 84 cuff seated SBP measurement. If the measurement at this visit is missing or the patient discontinues early, the last post-baseline measurement during the double-blind period will be used.

The primary efficacy analysis will be carried out using a 2-way analysis of covariance (ANCOVA) model with treatment, baseline eGFR level (≥ 30 versus < 30 mL/min/1.73 m²), and background antihypertensive medication (2 or more) as factors, and the baseline SBP value as a covariate. The least-squares means, standard errors, and the 2-tailed 95% confidence intervals (CIs) for each treatment group and for the comparison will be estimated. The treatment difference between KBP-5074 doses and placebo will be estimated from the ANCOVA model. No multiple comparison adjustment will be used for this Phase 2 study.

The primary efficacy analysis will be based on the ITT Population. Other imputation methods for the primary efficacy endpoint will be explored. The supportive analysis will be carried out for the primary efficacy variable based on the Per-Protocol Population to examine the impact due to premature dropouts and/or major protocol deviations or violations.

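### Does 80 patients per group fail the plan's own sizing rule at 15% dropout, and does the section hide a low chance of success?

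*Combined protocol and SAP*

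**What the plan says.** Section 9.2.7, repeated in the synopsis, assumes an observed difference of 5 mmHg between KBP-5074 and placebo in the change in SBP, with an SD of change of 15 mmHg. It first says that "with 80 patients/group, the CI of the observed difference would not include 0". The next sentence reads "Assuming 10% to 15% dropout post randomization, 80 patients/group or a total of 240 patients would be needed for this Phase 2 study".

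Table 2 then gives the "sample size needed per group to ensure that the observed 95% CI does not include 0" for SDs of 14, 15 and 16 mmHg and observed effects of 4, 5 and 6 mmHg. Its note says "Including approximately 10% to 15% dropout". The cell for SD 15 and 5 mmHg is 81. No power is stated, and no multiplicity adjustment is applied.

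Three other places determine whether a dropout is lost to the analysis:

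- Section 9.1 admits to the ITT Population treated patients with a baseline SBP who "have at least 1 post-randomization SBP measurement".
- Section 9.2.2.1 says that if Day 84 is missing or the patient stops early, "the last post-baseline measurement during the double-blind period will be used".
- Section 5.4 says "All patients will be asked to continue study visits to the end of the study whether or not they remain on study drug".

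**The concern.** Three things look wrong on a first reading.

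1. The same 80 is first the size at which the CI excludes 0, with no mention of dropout, and then the size that already allows for dropout. Table 2, which includes dropout, has 81.
2. The upper end of the stated dropout range appears to break the plan's only sizing criterion.
3. A design sized so that the observed target difference just clears 0 has about 50% power at that difference if it is the true one. A reader who meets the assurance that the CI will exclude 0 could take the trial to be reliably sized for 5 mmHg.

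If these points had force, the trial would be too small for its declared purpose, or its readers would be misled about what it can show.

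**Working it through.** **Inputs.** Observed difference 5 mmHg, SD 15 mmHg, 80 per group and 10% to 15% dropout (Section 9.2.7); two-tailed 95% CI (Section 9.2.2.1).

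**Step 1: analysed number needed.** The CI excludes 0 when 1.96 × SD × √(2/n) is below the difference, so n = 2 × (1.96 × SD / difference)². For the planning case, 2 × (1.96 × 15 / 5)² = 69.15, or 70 per group. A two-sample t version needs 71.

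**Step 2: reproduce Table 2.** The plan does not state its inflation rule. Multiplying the analysed n by 1.15 and rounding to the nearest whole number returns all nine cells:

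| SD (mmHg) | Effect (mmHg) | Analysed n | n × 1.15 | Table 2 |
|---|---|---|---|---|
| 14 | 4 | 95 | 109.25 | 109 |
| 14 | 5 | 61 | 70.15 | 70 |
| 14 | 6 | 42 | 48.30 | 48 |
| 15 | 4 | 109 | 125.35 | 125 |
| 15 | 5 | 70 | 80.50 | 81 |
| 15 | 6 | 49 | 56.35 | 56 |
| 16 | 4 | 123 | 141.45 | 141 |
| 16 | 5 | 79 | 90.85 | 91 |
| 16 | 6 | 55 | 63.25 | 63 |

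So 81 is 80.5 rounded up. A factor of 1.15 covers 1 − 1/1.15 = 13.0% loss, inside the stated range.

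**Step 3: what 80 covers.** 1 − 70/80 = 12.5%. Dividing 70 by (1 − loss) gives 78 at 10%, 80 at 12.5% and 83 at 15%.

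**Step 4: size of the shortfall.**

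- 80 analysed: SE = 15 × √(2/80) = 2.372; half-width 1.96 × 2.372 = 4.65 mmHg.
- 68 analysed (15% loss): SE = 15 × √(2/68) = 2.572; half-width 5.04 mmHg.

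The miss at 15% is 0.04 mmHg and 2 patients per group.

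**Step 5: can it happen in the primary analysis?** At 15% dropout, 12 of 80 leave. To fall below 70 analysed, at least 11 of those 12 must have no SBP after randomisation. The Day 7 visit already includes "Obtain blood pressure prior to study drug administration" (Section 6.4.3), and blood pressure is also taken at the Early Termination Visit (Section 6.6).

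**Step 6: chance that the CI excludes 0 if the true difference is 5 mmHg.** Φ(5/SE − 1.96):

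| SD (mmHg) | 80 analysed | 68 analysed |
|---|---|---|
| 14 | 62% | 55% |
| 15 | 56% | 49% |
| 16 | 51% | 45% |

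At SD 15, 80% power needs a true difference of 2.80 × SE: 6.6 mmHg with 80 analysed, 7.2 mmHg with 68.

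**Step 7: what Step 6 leaves out.** These are unadjusted figures for one dose against placebo. The planned model is an ANCOVA with baseline SBP as a covariate. With 68 analysed, a residual SD of 5 / (1.96 × √(2/68)) = 14.87 mmHg brings the half-width back to 5.0 mmHg. That takes a correlation between baseline and change of √(1 − (14.87/15)²), about 0.13. The documents give no correlation. If it were 0.3 to 0.5 (assumption), the chance at SD 15 would run from about 53% (68 analysed) to 68% (80 analysed). There are also two doses: if both truly gave 5 mmHg, the unadjusted chance that at least one CI excludes 0 is about 66% to 72%.

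**The case for a change.** The strongest case for a change is that CI exclusion of 0 is the only sizing criterion offered, and that the plan's own inflation treats dropout as loss, so the section should satisfy itself at 15%. In the supportive Per-Protocol analysis dropout really is full loss, because that population requires completion of 84 days, and Section 4.3 says withdrawn patients are not replaced. The roughly even chance at a true 5 mmHg is also useful to a reader and appears nowhere.

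The arithmetic behind all of this stands. Its weight does not. The Per-Protocol analysis is a robustness check and is not what the trial is sized for. Section 9.2.7 says openly that the difference is an observed one, claims no power, and shows how the size moves over a grid of SDs and effects; its assurance is true for the inputs it names. Accepting modest power in a Phase 2 estimation design is a fair trade-off.

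Printing the Step 6 figures as the trial's expected precision would bring a fault of its own. They ignore the baseline adjustment and the second dose comparison. Replacing the 10% to 15% range with a 12.5% ceiling would turn a forecast of dropout into a tolerance and remove the only dropout forecast in the plan.

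**Conclusion.** No change to the plan follows. The text's 80 and the table's 81 come from the same calculation, rounded differently, and differ by one patient per group in a trial described in Section 3.1 as enrolling approximately 240. The dropout allowance holds up to 12.5% and misses at 15% by 0.04 mmHg of half-width, which under the ITT rule with last value carried forward would need nearly every dropout to have no SBP after randomisation.

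The unstated 49% to 56% chance at a true 5 mmHg is a real omission of detail, but no planned analysis, decision rule or conclusion depends on it, and any statistician can derive it from the inputs given.

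This rests on the normal approximation with whole patients. The tolerable loss is 11.25% with a two-sample t and 13.6% with the unrounded n of 69.15. It also rests on an SD of 15 mmHg and on an inferred rule for Table 2.
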